13.4 Serious Adverse Event Listings

At the end of the trial, listings of SAEs will include the relatedness of the event to the study, the outcome of the SAE, gender, age, and ethnicity for the participant. All interim reports will present these events in a blinded manner unless otherwise specified by the DSMB.

13.5 Sample Size Estimate

Because this is a feasibility study, we had 3 major considerations: to complete the study in a timely manner, to keep the costs low, and to recruit as many participants as possible within these constraints. Thus, rather than statistical power guiding the sample size decision, real-life research constraints were invoked. In terms of study timeline, the duration of enrollment is anticipated to be 9–12 months in order to give the CTPs ample time to become familiar and competent with the study protocol, so that in addition to

months reflecting start-up, we would have data for several months that reflect the full potential of the CTPs to recruit participants. Each CTP is expected to randomize about 60 to 120 participants across the recruitment period. Thus, 360 participants are estimated for the total sample size across CTPs.

Not all individuals who agree to participate will complete their residential treatment episode, and an additional number will fail to meet the eligibility criteria for the study. Based upon program experience, we expect approximately 25% of participants to fail to complete their residential treatment, and an additional 15% to fail to meet the eligibility criteria of the study. Thus, if 16 participants per month agree to participate, we would expect 12 to complete their residential treatment, and approximately 10 to meet the eligibility criteria of the study. Based on these numbers, we expect that approximately 4 participants per week will agree to participate at each CTP (at intake to the residential program).

13.6 Post Hoc Analysis

During the course of conducting the primary and secondary summaries, the data may suggest other interesting differences by CTP or treatment group. Post hoc analyses are anticipated to explore these findings. One potential post hoc analysis would be the exploration of factors found to be significantly different between groups at baseline, as they relate to study outcomes. Other potential post hoc analyses would be the exploration of the effects of gender and site on outcomes. Additionally, a comparison of baseline characteristics between participants who are randomized and those contacted for follow-up will be completed for generalization of the conclusions.

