In the feasibility study, 4 sites will conduct the procedures outlined in this protocol. Procedures have been designed by the TELE protocol group and approved by the Clinical Trials Network (CTN) Steering Committee. The feasibility study will include 360 randomized participants—180 per treatment condition. Each of the sites is expected to randomly assign 60 to 120 participants. If the study shows that it is feasible to deliver the telephone calling intervention and to collect adequate data to compare with a control group, and there is evidence to suggest positive effects of the intervention, recommendations will be made to the CTN Steering Committee for a large-scale trial evaluating the efficacy of the TELE procedure.

The feasibility study will be conducted as follows:

Candidates eligible for randomization will include men and women enrolled in residential substance abuse treatment programs for at least 7 days but no more than 42 days. Participants must be at least 18 years of age and have the ability to understand and provide written informed consent. In addition, they must have been voluntarily admitted (not civilly committed) to the rehabilitation regimen (not admitted for detoxification only) and have a diagnosis for substance abuse or dependence as determined by residential program admission information. Referrals must be from a program servicing the targeted counties at the time of admission, and participants must plan to return to residence in the target counties after their discharge from the residential treatment program. Participants must have no evidence of current suicide intention or recent (\leq 30 days prior to admission) suicide attempt and must complete study requirements prior to departure from the program. All participants must have a working telephone number for contact after their discharge.

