5.2 Efficacy

A secondary goal of this feasibility study is to explore the impact of the TCG condition on participation in post-discharge continuing care activities. In addition, we will examine whether the TELE procedure results in reduced drug and alcohol use of study participants as measured by urinalysis, breath alcohol test, or self-report. Insofar as this study is not adequately powered to answer these experimental questions, the analysis of the TELE efficacy data from the 4 sites will be used to support the conduct of a future full-scale trial and to provide a basis for effect size and power calculations in the future study.

These are specific aims of the secondary analysis:

1. To compare the effect of TCG condition with that of the SCG condition on the basis of participant involvement in aftercare programs. We believe that, compared

with SCG participants, TCG participants will have an increased participation in continuing care activities.

2. To compare drug and alcohol use measures at 13 weeks post-discharge in the telephone call group (TCG) and standard of care group (SCG). We believe that those who receive the telephone calls will have a higher rate of drug/alcohol abstinence at the follow-up visit.

To determine the effect of the TELE procedure, the following measures will be collected at the 13-week post-discharge follow-up visit:

- Self-reported engagement in continuing care activities prescribed in the continuing care plan prepared by the residential treatment program
- Drug use as measured by urine test
- Alcohol use as measured by breath alcohol test
- Drug and alcohol use during the past 30 days as measured by the CTN Addictive Severity Index-Lite (ASI-Lite) Follow-up Version 1 Form
- Other measures of functioning from the CTN ASI-Lite Follow-up Version 1 Form

The analysis of these data will provide a preliminary overview of the clinical effectiveness of the regimen of telephone calls. Information from this study can then be used to design a full-scale clinical trial.

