11.3 HIV Risk Behaviors Survey

The Risk Behavior Survey (RBS), an abbreviated version of the Risk Behavior Assessment (RBA) developed by NIDA for the Cooperative Agreement, will be used to measure risk behaviors related to human immunodeficiency virus (HIV) and hepatitis C virus (HCV). Risk behaviors in the areas of drug use and sex in the previous 30 days are measured. Reliability and validity assessments of the RBS support its adequacy as a research tool for populations of drug users, including intravenous drug users (Darke et al., 1991; Weatherby et al., 1994; Needle et al., 1995).

11.4 CTN Addiction Severity Index-Lite Version 1 and Follow-up Version 1

The CTN Addiction Severity Index-Lite Version 1 and Follow-up Version 1 forms are multidimensional, semi-structured, comprehensive clinical interviews, which provide clinical information important for formulating treatment plans, as well as problem severity profiles in 6 domains commonly affected in substance abusers (McLellan et al., 1985). The domains covered are chemical abuse (alcohol and drug), medical, psychiatric, legal, family/social relations, and employment/support status. Composite scores for each problem domain are derived mathematically and used as change measures or outcome indicators as a function of treatment intervention.

These instruments also provide clinically necessary information on whether the participant is at imminent risk for suicide, thus permitting evaluators to implement any

needed immediate and/or early intervention strategies. The CTN ASI - Lite forms will be administered by a research staff member with a bachelor's degree in the social sciences or equivalent training and experience, as determined by the site's investigator. Composite scores will be calculated according to the procedures described by McGahan et al. (1982), and Carroll et al. (1994).

The CTN ASI - Lite Version 1 form will be administered during the baseline assessment and the CTN ASI - Lite Follow-up Version 1 will be administered at the 13-week follow-up visit.

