13.2 Feasibility Indicators

Feasibility information will be gathered to determine the proportion of (1) total eligible participants who volunteer and thus consent to participate in the study, (2) consenting participants completing all required residential treatment and baseline assessments, (3) consenting participants meeting the eligibility criteria, (4) consenting participants randomized into one of the 2 treatment conditions, (5) randomized participants contacted by phone after discharge, (6) randomized participants who could be contacted for follow-up visit, and (7) randomized participants completing the follow-up during the visit.

In order to determine 1–7 above, we will need to collect the following information:

- Number of participants entering the residential program
- Number asked to participate in the protocol
- Number agreeing to participate in the protocol
- Of those who agree, the number who complete the baseline assessments
- Of those who agree, the number who complete the residential program

- Of those who complete the residential program, the number who meet eligibility criteria for the study
- Number of participants randomly assigned to a treatment group;
- Number of patients successfully contacted to schedule week 13 visit
- Number of week 13 visits completed for the randomized patients
- Of those who complete a week 13 visit, time interval between discharge and the follow-up visit

For the TCG participants, logs of phone calls and attempted contacts will be compiled to examine the proportion of participants in which the 7 phone contacts were delivered and the average number of phone contacts delivered per participant. To determine whether it is possible to reach participants by telephone after they have been discharged from residential substance abuse care, the following data will be collected:

- Number of scheduled phone contacts attempted
- Number of scheduled phone contacts completed (delivered)

For the TCG condition, fidelity procedures have been included in the study to evaluate whether counselors who deliver the calls can conduct these calls in a standardized manner when provided with a structured "script." A portion of calls will be recorded and at least 10% of successful calls will be randomly selected by the Lead Node statistician for analyses for treatment integrity and fidelity.

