Equality of treatment groups at baseline will be evaluated by comparing demographic and drug-use information collected on the CTN ASI-Lite Version 1 and Follow-up forms. Baseline demographic values that potentially affect the responses or are found to be unevenly distributed between groups at baseline despite randomization may be investigated in supplementary analyses. Baseline values are not planned to be covariates in any analyses because sample sizes are expected to be too small. Where possible, treatment effects will be summarized by gender, ethnicity, and age group separately.

A summary will be prepared to show dropouts/retention over time in each treatment group. The number of missing observations will be compared between treatments. In the analysis of the effect of the telephone call regimen on the participant abstinence (objective measure by urinalysis & breathalyzer), participants lost to follow-up at 13 weeks will be handled in 2 different approaches in an attempt to elucidate the influence of missing data on interpretation of the results. In the first analysis, participants lost to follow-up at 13 weeks will be considered "non-abstinent" to account for the possibility that non-abstinent participants may be more likely to be lost at follow-up. In the second approach, participants lost to follow-up at 13 weeks will be considered as missing. We anticipate that the category "missing at follow up" will account for 20% or fewer of randomized participants. Effects of gender and substance use diagnosis will be investigated in a supplementary analysis.

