13.7 Randomization

Randomization (1:1 treatment allocation) will be performed using a randomized block design, stratified by site. This will enable sites to enroll differing numbers of participants while maintaining a fairly close balance between groups within sites. One of the outcomes of this feasibility study is the measure of whether the CTPs are capable of enrolling the expected numbers. Thus, some of the CTPs may not enroll the expected number, and we will employ blocking in order to preserve our ability to examine existent data at the end of the study. Block size will be determined by the statistical group at the Lead Node who will prepare the randomization scheme.

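### The baseline-balance check draws on the week-13 ASI-Lite Follow-up form, and the follow-up comparison sets all randomized participants beside a subset of themselves

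*Protocol*

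**What the plan says.** **Baseline balance.** Protocol Section 13.3.1 evaluates equality of the treatment groups at baseline by "comparing demographic and drug-use information collected on the CTN ASI-Lite Version 1 and Follow-up forms". Section 11.4 assigns Version 1 to the baseline assessment and states that "the CTN ASI - Lite Follow-up Version 1 will be administered at the 13-week follow-up visit"; Table 3 agrees. Section 5.2 lists among the measures of the effect of the procedure "Drug and alcohol use during the past 30 days as measured by the CTN Addictive Severity Index-Lite (ASI-Lite) Follow-up Version 1 Form".

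**Follow-up comparison.** Section 13.6 says that "a comparison of baseline characteristics between participants who are randomized and those contacted for follow-up will be completed", and gives generalization of the conclusions as the purpose. Section 13.2 takes contact and completion as separate feasibility indicators, both counted among the randomized: "randomized participants who could be contacted for follow-up visit, and (7) randomized participants completing the follow-up during the visit". Section 13.3.1 expects that those missing at follow-up "will account for 20% or fewer of randomized participants".

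**The concern.** A baseline-balance check should use only information recorded before the intervention can act. The Follow-up form is completed after the calls and only by those who attend. If its drug-use items enter the check, a real effect of the calls, or a difference between arms in who attends, can appear as imbalance. Section 13.6 then offers, as one possible post hoc analysis, exploring factors that differ between groups at baseline in relation to outcome. On the literal wording, that could mean relating an outcome to itself.

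The second comparison uses the right data, namely baseline characteristics, but an insensitive pair of groups. The second group lies inside the first, so most of the people compared are the same people. Membership also turns on contact rather than on having a week-13 assessment, so a participant who was reached but did not attend counts with the followed. Section 5.1 makes sufficient and equivalent follow-up data a critical aspect of feasibility, and Section 13.3.1 itself raises the possibility that non-abstinent participants are lost more often. A clear view of who was lost is therefore worth having.

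**Working it through.** The protocol gives no figure for either comparison, so there is none to reproduce.

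**A. Balance check: the sections side by side**

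- Section 13.3.1: balance at baseline, from Version 1 and the Follow-up form.
- Section 11.4 and Table 3: the Follow-up form is given at the follow-up visit only.
- Table 1: calls run from day 4 to day 87 after discharge; the visit falls on days 88–116.
- The form covers drug and alcohol use in the past 30 days. For a visit on day 88 that period begins at day 88 − 30 = 58, so it spans the windows of call 6 (days 67–73) and call 7 (days 81–87). For a visit on day 116 it begins at day 86.

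The Follow-up form cannot describe drug use at baseline, and no other section corrects the wording.

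**B. Follow-up comparison: dilution**

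Inputs from the protocol:
- 360 randomized (Section 3.0: "The feasibility study will include 360 randomized participants").
- 20% missing at follow-up, used as the ceiling (Section 13.3.1), so 360 × 0.20 = 72 lost and 288 followed.

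Assumptions, not protocol figures:
- A baseline characteristic is present in 50% of the followed and 70% of the lost.
- Two-sided 0.05 where a test is illustrated; the protocol sets no significance level.

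Let F and M be the means in the followed and the lost, and L the lost fraction. Then

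All = (1 − L)F + L·M, so All − F = L(M − F).

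At L = 0.20: All = 0.80 × 50 + 0.20 × 70 = 54%. The display shows 54% against 50%, or 4 points, where the followed and the lost differ by 20. For the same 20 points:

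| Lost fraction | Points shown |
|---|---|
| 5% | 1 |
| 10% | 2 |
| 20% | 4 |
| 30% | 6 |

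**C. Contacted is not completed**

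The 20% is the share missing at follow-up; the protocol gives no share for those not contacted. Suppose, as an assumption, that half of the 72 (36) were contacted but did not attend, and that they too have the characteristic in 70%. The contacted group is then 288 + 36 = 324, with (144 + 25.2)/324 = 52.2%. Against 54% for all randomized, the display shows 1.8 points.

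**D. If an independent-groups test were run**

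- Naive test, 360 against 288: the pooled proportion is (194.4 + 144)/648 = 0.522, and the standard error is √(0.522 × 0.478 × (1/360 + 1/288)) = 0.0395. The expected z is 0.04/0.0395 = 1.0.
- The true standard error of that difference is 0.20 × √(0.25/288 + 0.21/72) = 0.0123, about a third of what the naive test assumes.
- Disjoint groups, 288 against 72: the standard error is √(0.54 × 0.46 × (1/288 + 1/72)) = 0.0657, so the expected z is 0.20/0.0657 = 3.0.

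In 200,000 simulated trials the naive test rejected in about 0.1%, and the disjoint comparison in about 87% (0.88 by formula). With no true difference, the naive test did not reject in any of the simulated trials, and the disjoint test rejected in 4.8%.

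**The case against.** Much can be said for the plan, and part of it stands.

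- **The balance wording may be a slip.** The sentence is about equality at baseline and echoes the paired title of Section 11.4, while Table 3 is clear on timing. A slip is the likelier reading, but an analyst following the text would still include the form.
- **A reader might infer that the plan adjusts for a post-treatment variable.** It does not. Section 13.3.1 says that baseline values are not planned covariates, and limits the supplementary investigation mentioned there to demographic values. The remaining route is the possible post hoc exploration in Section 13.6.
- **Showing the followed beside all randomized is a legitimate display of representativeness**, which is the stated purpose. With both columns and their sizes, the lost group can be recovered: M = (54 − 0.80 × 50)/0.20 = 70%. This stands: the difference is diluted on the page, not destroyed. The reader must still do the back-calculation, and by contact rather than completion.
- **A reader might infer that an invalid test is planned.** Section 13.6 names none, so part D of the working is conditional.
- **A reader might infer that selective loss would go unnoticed.** Section 13.3.1 also plans a retention summary by arm, a comparison of missing observations between arms, and two handlings of loss in the abstinence analysis. None of these compares the baseline characteristics of the lost with those of the followed, but Section 13.6 is not the only safeguard.

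**Conclusion.** Both points hold as faults of wording that would weaken supporting analyses if followed literally.

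The balance check names an outcome form collected at week 13. This follows from the text alone and needs no assumption.

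The follow-up comparison is valid as a display but insensitive. It shows only the lost fraction of any difference between followed and lost: one fifth at 20% loss, and less if some of those contacted never attended. The identity is exact. The 50% and 70% rates, the half-contacted split and the 0.05 level are illustrations.

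The impact is limited. Section 13.3.1 treats the efficacy tests as exploratory, the Section 13.6 comparison is post hoc, and no formal covariate adjustment is planned. Neither point alters a main efficacy comparison. Both should be corrected, because the corrections use data already being collected.

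**What to change.** - **Section 13.3.1:** delete the words *and Follow-up*, so that the ASI-Lite information used to judge baseline balance comes from the Version 1 form only.
- **Section 13.6:** replace the planned comparison with one of baseline characteristics between randomized participants with and without a completed week-13 visit, presented descriptively, overall and by arm. A column for all randomized may stay alongside for generalization. With "Randomization (1:1 treatment allocation) will be performed using a randomized block design, stratified by site", there are 180 per arm, so at the 20% ceiling about 36 per arm would be lost. That is enough to describe; a formal test of whether loss differs by arm and baseline severity is optional.

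The cost is two sentences. No new data, visits or change of design are needed.

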13.7 Randomization

Randomization (1:1 treatment allocation) will be performed using a randomized block design, stratified by site. This will enable sites to enroll differing numbers of participants while maintaining a fairly close balance between groups within sites. One of the outcomes of this feasibility study is the measure of whether the CTPs are capable of enrolling the expected numbers. Thus, some of the CTPs may not enroll the expected number, and we will employ blocking in order to preserve our ability to examine existent data at the end of the study. Block size will be determined by the statistical group at the Lead Node who will prepare the randomization scheme.

14.0 DATA MANAGEMENT AND CASE REPORT FORMS

14.1 Data Collection

Database management and quality control for the TELE trial are the responsibility of the Duke Clinical Research Institute (the Lead Node Data Management Center).

The investigators will collect information required by the protocol on case report forms (CRFs). Data on subjects collected on CRFs during the trial will be documented in an

anonymous fashion, and the subject will only be identified by the subject number and by his or her initials. Upon completion, the CRFs will be forwarded to the Lead Node Data Management Center.

All information required by the protocol should be obtained and any omissions should be explained. CRFs should be completed on an ongoing basis during the study according to the instructions provided during training. The investigator is responsible for maintaining accurate, complete and up-to-date records for each participant. The investigator is also responsible for maintaining any source documentation related to the study, including any items such as recordings, computer discs, or tapes.

14.2 Data Accrual, Editing and Control

Completed CRFs will be submitted on a regular basis to the Data Management Center at Duke Clinical Research Institute. Upon receipt of the CRFs, the Data Management Center will process them according to DCRI standard operating procedures. Quality control methods will be utilized throughout the process to maintain the data's integrity (see section 12.3.4).

When data is received at the Data Management Center, it will be reviewed, and if incomplete or inaccurate data are found, a Data Clarification Form (DCF) will be forwarded to the sites for a response. Sites will resolve data inconsistencies and errors prior to returning data to the Data Management Center. All corrections and changes to the data will be reviewed prior to being entered into the study database.

When there are no required or expected outstanding queries, and all expected data has been received, the database will be locked. Any changes to the database after that time can only be made by joint written agreement between the Lead Node project leader, the Lead Node trial statistician, the Lead Node data manager, and a NIDA representative.

